Patients who respond to initial ACT+CM treatment may benefit from continued ACT to prevent relapse. Achieving early cocaine abstinence is a robust predictor of longer term cocaine abstinence.³³ In our previous feasibility study, patients who achieved two consecutive weeks of abstinence under high-magnitude CM used less cocaine during subsequent treatment, regardless of medication received, compared with subjects who failed to achieve initial abstinence.¹² However 15 of the 33 initial responders (46%) “relapsed” during second treatment, as indicated by the first cocaine-positive urine after achieving initial abstinence. Using 46% as a benchmark for measuring improvement, the goal of the proposed study is to construct an optimal adaptive treatment intervention that reduces relapse (<46%) within this subgroup of initial responders with an otherwise good prognosis.

As mentioned, CM interventions that provide high-magnitude alternative sources of reinforcement have been quite effective in promoting initial, *externally*-motivated, changes in behavior. The long-term efficacy of incentive-based treatments in reducing relapse is less clear. For CM, like most interventions, the magnitude of the treatment effect declines over time.¹¹ Indeed, one of the most oft-cited concerns with CM has to do with maintenance of behavior change after reinforcement is discontinued or faded. The notion of extending CM according to an “incentives maintenance model”, has been suggested,³⁴ however studies of longer CM interventions have shown lower effect sizes on average than shorter CM interventions.¹¹ Rather, the common clinical practice is to combine CM with other interventions that focus on sustaining initial treatment gains and minimize relapse risk. Relapse is commonly triggered by aversive internal experiences such as negative affect, stress, craving, and other withdrawal symptoms that can occur during and well beyond the acute phase of cessation.³⁵ To the extent that avoidant responding to these aversive states is a mechanism underlying cocaine relapse, acceptance-based therapy goals, as described above, are well-suited for relapse prevention. Another major goal of ACT is to help the patient **develop** sustainable, **value driven, goal-directed** approach behaviors as an alternative to avoidance.³⁶ Learning and practicing to choose behaviors based on important personal values and goals rather than choosing to focus on the immediate reduction of craving, negative affect, or stress, will decrease relapse risk. ACT-based strategies may play an essential role in the maintenance of drug abstinence by shifting patients’ motivation from external (e.g., CM) to internal incentives or sources of motivation.

In summary, the proposed SMART design represents a significant departure from standard randomized clinical trial paradigms that fail to address the heterogeneity of treatment response seen among individuals with chronic CUD. Continued progress in treatment development research must overcome this barrier with novel trial designs that formalize clinical decision making, thus having a real-world impact on the treatment of cocaine addiction and other chronic substance use disorders.

Aims and Hypotheses

[figure not shown]
1. To determine if ACT enhances response to a high-magnitude CM procedure targeting cocaine-negative urines. It is hypothesized that initial treatment (4 weeks) with ACT and CM (ACT+CM) will produce higher response (abstinence) rates than initial treatment that combines standard Drug Counseling with CM (DC+CM).
 - 1.a. To determine if pretreatment EA level moderates the effects of ACT+CM on initial response. It is hypothesized that the benefit of ACT+CM over DC+CM on initial response (abstinence) rates will be greater in the subgroup of individuals with higher pretreatment EA scores.
 - 1.b. To determine if the effects of ACT+CM are mediated by changes in EA and reward sensitivity. It is hypothesized that ACT+CM effects on initial treatment response will be mediated by the primary hypothesized treatment mechanisms, EA and reward sensitivity.

Secondary Aims/Hypotheses:

2. To determine the best sequencing of treatment for initial non-responders. For initial non-responders, it is hypothesized that continued ACT+CM treatment with pharmacotherapy (modafinil) augmentation will be most effective in promoting abstinence relative to treatment combinations involving DC and/or placebo.
3. To determine the best sequencing of treatment for initial responders. For initial responders, it is hypothesized that continued ACT+CM will be more effective (higher abstinence rates; < 46% relapse rate) than continued DC+CM.

Study Design

Overall Research Strategy. We propose an adaptive, two-stage SMART design to test the primary research hypothesis that ACT, when used in combination with CM, will increase initial treatment response rates. Secondary hypotheses will determine the probability of benefit associated with two sequences of treatments, specifically, continued ACT+CM for initial treatment responders (dashed lines in **Figure B.3.2.i**) and continued ACT+CM with modafinil augmentation for initial treatment non-responders (double lines in **Figure B.3.2.i**).

Overview of Study Design. Note: SR=stratified randomization; R=randomization; ACT=Acceptance and Commitment Therapy; DC=Drug Counseling; CM=Contingency Management; PLA=placebo; MOD=modafinil. Abstinent=6 consecutive (2 wks) cocaine-negative (BE<150 ng/ml) urines samples.

Participants. The study will enroll treatment-seeking individuals, 18 to 60 years old, who meet current DSM-5 criteria for CUD of at least moderate severity (≥ 4 symptoms). Eligible subjects must submit at least one positive urine toxicology screen for the cocaine metabolite (BE ≥ 150 ng/mL) during intake; a standard requirement in most cocaine trials to ensure enrollment of patients actively using cocaine. Subjects meeting moderate or severe criteria for substances other than cocaine, marijuana, alcohol, or nicotine will be excluded. Subjects whose alcohol use meets for physiological dependence requiring detoxification or use that makes participation medically unsafe as determined by the medical director will be excluded. Other exclusion criteria will include the presence of significant and unstable psychiatric disorders, including active psychosis, dementia, or other axis I psychiatric or neurological conditions requiring ongoing treatment and/or making study participation unsafe. Individuals with a past psychiatric history but without symptoms reported within the past 12 months prior to assessment, and who meet other inclusion criteria, may be eligible to participate. Individuals having medical conditions (e.g., severe cardiovascular disease, severe liver impairment) or taking medications (e.g., propranolol, phenytoin, warfarin, or diazepam) known to be contraindicated for modafinil pharmacotherapy will be excluded. To be eligible, females of childbearing potential must agree to use an acceptable method of birth control during study participation and for one month after discontinuation of the study medication. Non-hormonal methods of contraception are recommended, including barrier contraceptives (e.g., diaphragm, cervical cap, male condom) or intrauterine device (IUD). Steroid contraceptives if used with non-hormonal methods are acceptable. No pregnant women will be permitted in study. There will be separate inclusion/exclusion criteria for the Electroencephalogram (EEG) sub-study. Individuals with hairstyles that are incompatible with an EEG net (e.g., tight braids, ponytails, wigs, weaves, dreadlocks, or head scarves, etc.) and are unwilling to change the hairstyle will be excluded only from the EEG portion of the study. Individuals will also be excluded if they have a history of epilepsy or seizure disorder or head injury with loss of consciousness in the past 5 years.

Eligibility criteria (described above) will be evaluated as part of the General Evaluation protocol for all treatment research studies at our clinic. All potential subjects are invited to first participate in this

separate CPHS-approved protocol (**HSC-MS-05-0322 - "General Evaluation of Eligibility for Substance Abuse/Dependence Research**). Intake evaluation procedures will include a complete psychiatric diagnosis using the Structured Clinical Interview for DSM-5 (SCID-5) administered by trained licensed professional counselors under the supervision of a licensed clinical psychologist. Medical screening will include a history and physical examination, a blood draw for serum chemistry and blood count, urine sample for urinalysis and an electrocardiogram (EKG), and urine testing for drugs of abuse and pregnancy. Lab tests will include a Comprehensive Metabolic Panel (CMP) with tests of liver enzymes: alkaline phosphatase (ALP), alanine amino transferase (ALT), aspartate amino transferase (AST), Prothrombin time (PT), partial thromboplastin time (PTT), and bilirubin. We will apply the Child-Pugh criteria to exclude subjects with stage B or C scores, indicating severe liver disease. Upon completion of this intake evaluation, eligible participants will be invited to participate in the current study.

Study Site, Recruitment, Projected Enrollment. The study site is the Treatment Research Clinic of the Center for Neurobehavioral Research on Addictions (CNRA), a university-supported center of excellence within the UT-Houston Department of Psychiatry and Behavioral Sciences and a NIDA-funded Medications Development Center (P50 DA 009262). Since 1995, the CNRA has been the site for more than 20 randomized clinical trials, enrolling over 1,000 patients with substance use disorders, most of these with CUD. Established and effective recruitment strategies have been identified ³⁷ and will be used, including newspaper/newsletter articles, public service announcements on TV and radio, notices mailed to local professionals, and billboards located throughout the local community. We will reach our projected enrollment of N=160 subjects within 40 months, based on our established record of enrolling 4 new subjects per month on average; a rate we have maintained for the past 5 years.

Phase 1 treatments. Consenting subjects will be assigned to one of the two 4-week Phase 1 treatments, ACT+CM or DC+CM, using urn randomization to ensure balance between groups on baseline EA level, coded as "high" if AIS score > 45, or "low"≤ 45. Subjects in both treatments will be scheduled to attend three clinic visits per week (MWF) during the 4-week period. **Two** of these weekly visits will include 1-hour therapy sessions (ACT or DC).

Acceptance and Commitment Therapy-Cocaine Use (ACT). The overarching goal of ACT is to decrease experiential avoidance while increasing acceptance and willingness to experience unpleasant thoughts, feelings, and physical symptoms. More specifically, ACT will assist cocaine patients to notice their internal cravings and triggers, abandon their attempts to manage these triggers via active avoidance, suppression or other control-based strategies, and to make commitments to engage in behaviors consistent with their chosen values or goals. ACT encourages clients to experience thoughts and feelings from an observer perspective, and helps them not to believe distressing thoughts and feelings as if they are literally true and in need of action. ACT treatment will be based on the therapy manual developed and tested previously.^{38, 39} The manual covers 10 core topics listed in **Table B.3.2.vi.** Our experienced ACT therapists will be taught to use the manual as a map with flexibility to "go with the client" so long as issues of acceptance, diffusion, values, and committed action are thoroughly covered. Mindfulness exercises, metaphors, and homework sheets will be used to pursue therapeutic goals, more so than didactic instruction. Masters-level therapists with ACT experience from our previous trial ³⁸ will be trained and supervised by [name] (Co-I) and [name] (Consultant).

Drug Counseling (DC). We will use the manual-guided individual DC modeled after the NIDA Collaborative Cocaine Treatment Study ⁴⁰ and used as the active control therapy in our previous studies.^{38, 41, 42} DC approximates clinical practice as it is considered the most common type of evidence-

based treatment in the community for patients actively using cocaine. DC educates patients about important concepts in addiction recovery based on the underlying philosophy that physical, emotional, spiritual, and interpersonal needs must all be addressed to support recovery. Accordingly, the DC manual covers the core topics listed in **Table B.3.2.vi**. Masters-level therapists with DC experience from our previous trials^{41, 42} will be trained and supervised by [name] (Co-I).

Contingency Management (CM). We will use the same high-magnitude CM schedule shown previously to be feasible and effective in facilitating initial cocaine abstinence.¹² Subjects will earn vouchers for cocaine-negative urine samples collected at scheduled clinic visits (MWF) each week. Under an escalating reinforcement schedule, voucher values will begin at \$15 and increase by \$10 for each consecutive negative urine. Provision of a cocaine-positive urine or failure to provide a scheduled sample will result in no vouchers earned and will reset the schedule to the initial value (\$15). Bonus vouchers (\$10) will be given for completing all study-related tasks in a given week. Subjects will redeem their earned vouchers for cash loaded to the ClinCard, a reloadable debit card.

Initial response and re-randomization. Following Phase 1 treatment, the primary outcome of response/non-response will be determined. Subjects who submit 6 consecutive (2 weeks) cocaine negative urine samples by week 4 will be classified as responders. Those who fail to meet response criteria will be classified as non-responders.

During second (Phase 2) treatment:

- Responders will continue to receive their assigned initial treatment, as described below.
- Non-responders in each initial treatment arm will be re-randomized to a second treatment consisting of pharmacotherapy augmentation with either modafinil or placebo.

All subjects will attend three clinic visits per week (MWF) during the 8 week second treatment period.

Table B.3.2.vi. 10 Core Topics for ACT and DC

Second (Phase 2) treatments	ACT	DC
Continued ACT or DC. Twice weekly 1-hour ACT and DC sessions will continue during the 8 weeks of second treatment, covering the core topics shown in Table B.3.2.vi.	Preparing to begin	Planning my recovery
	Values	Stages of recovery
	Making contact with the cost of using	People, places, things
	Creative hopelessness	Self-help groups & support systems
	Control v Willingness	Establishing a support system
	Defusion & Deliteralization	Spirituality
	Distinguishing the person from the programming	Personal Inventory
	Barriers to valued action	Character Defects
	Making a commitment	Lifestyle evaluation
Contingency Management.	Maintaining a commitment	Employment and managing money

CM during Phase 2 treatment will continue to offer subjects the opportunity to earn rewards for engaging in targeted behaviors for either cocaine abstinence or session attendance based on initial treatment response.

Initial treatment non-responders will receive abstinence-based CM using the standard prize bowl method described by Petry who switched to this lower-cost procedure after one month of high-magnitude CM for patients who initiated treatment with cocaine-positive urines.¹⁵ Patients will earn draws every time they submit a cocaine-negative urine at clinic visits (MWF). Draws will escalate by one for each consecutive negative urine sample, up to a maximum of 7 draws per day. Missed visits without a valid excuse will reset draws to one the next time attended. Reset value will return to the highest previously achieved value if patients attend fully for 3 consecutive visits. The standard prize bowl will contain 500 slips with 50% associated with small prizes. Of these, 209 will be small (\$5) prizes, 40 will be large (\$20) prizes, and one will be a jumbo (\$100) prize. Patients will receive earned prizes immediately in the form of cash loaded to the ClinCard, a reloadable debit card provided by UTHealth.

Phase 1 treatment responders will receive attendance-based CM using the same prize bowl method described above. The Petry study found that for initially cocaine-negative patients, reinforcing attendance was as efficacious as an abstinence-based CM in promoting longer durations of abstinence.¹⁵

Pharmacotherapy augmentation. We chose modafinil as the pharmacotherapy augmentation strategy for non-responders based on growing and encouraging evidence from numerous clinical trials in cocaine dependent treatment-seeking patients.^{29, 31, 32, 43} Its dopaminergic and glutamatergic activity make sense theoretically for non-responders who likely represent a subgroup with greater biological/neurochemical impairment and for whom behavioral interventions alone may not sufficiently change dopamine transmission.²⁴ Modafinil will start at 200 mg (day 1) and increase to the fixed dose of 300 mg (day 2). Placebo capsules will be identical in size, color, coating and shape. Participants in both conditions will take the same number of capsules at the same scheduled times (morning/evening) per day throughout treatment. Capsules will be packaged in blister cards with emergency replacement cards provided in the event that a subject forgets to bring their weekly card to the clinic or to replace lost cards. On clinic visits (MWF) the morning dose on the blister card will be taken by the subject at the dispensing window under observation by study staff. Additional standard methods for monitoring medication compliance will be followed, including pill counts and analysis of urine samples for riboflavin. Compliance will be defined using a cutoff level ≥ 20 fluorescence units, consistent with Mooney et al.⁴⁴ and our previous medication trials.^{12, 45, 46}

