exist. Posterior distributions can then be used as informative priors for continued monitoring in expansions of treatments and treatment strategies exhibiting initial promise.

Analytic strategy. Broadly, the analytic strategy will use generalized linear modeling. Continuous, dichotomous and time-to-event data will utilize linear, logistic, and proportional hazards regression respectively. Longitudinal analyses will employ generalized linear mixed models. All of these SAS (ver 9.3) procedures permit Bayesian analyses. Primary analyses will use intention-to-treat principles, with missing observations imputed as positive. Secondary analyses will implement joint modeling of observed outcomes and the missing data which is robust to ignorable missingness.^{81, 82} Sensitivity analyses will evaluate robustness of analytic conclusions to missing data. Non-ignorable missing data patterns will be addressed through pattern-mixture modeling methods.⁸¹ Prior distributions for comparison of proportions will use $\sim \text{Beta}(a = 1, b = 1)$ priors. Linear, logistic and Cox Proportional Hazards regression coefficient priors will take the form $\sim \text{N}(\text{mean} = 0, \text{var} = 1 \times 10^6)$ in the linear, log (odds) and log scales respectively. Level one error variances will be specified as $\sim \text{Inverse Gamma}(\text{shape} = 0.001, \text{scale} = 0.001)$; level two variances will use $\sim \text{Uniform}(0, 1000)$ distributions. Sensitivity analyses using optimistic and pessimistic, skeptical priors will evaluate prior assumptions.^{83, 84} Inverse probability weight will permit unbiased effect size estimates in the context of re-randomization. Finally, coding procedures will permit identification of each salient effect. Specifically, at the initial randomization ACT+CM and DC+CM will be coded as 1 and -1 respectively. For the re-randomization: 1) non-responders receiving continuation therapy will be coded 1 while all other participants will be coded 0; 2) non-responders receiving augmentation will be coded 1 versus 0 for all other participants.

Hypothesis testing.

Hyp. 1. Initial treatment with ACT+CM will produce higher response (abstinence) rates than initial treatment with DC+CM. Logistic regression will evaluate cocaine-abstinence rates at week 4 as a function of treatment assignment.

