Hyp. 1.a. The benefit of ACT+CM over DC+CM on initial response (abstinence) rates will be greater in the subgroup of individuals with higher pretreatment EA scores. Adding the interaction term (EA-by treatment) to the logistic regression model will evaluate the moderating effect of EA.

Hyp. 1.b. ACT+CM effects on initial treatment response will be mediated by the primary hypothesized treatment mechanisms, EA and reward sensitivity. In the context of the direct effect of treatment on response, mediational modeling will evaluate the *indirect* effect of treatment on response via EA and reward sensitivity variables, using the product moment method with bootstrapped 95% CI and Bayesian posterior distributions.

Hyp. 2. For initial non-responders, continued ACT+CM treatment with pharmacotherapy (modafinil) augmentation will be most effective in promoting abstinence relative to treatment combinations involving DC and/or placebo. Logistic regression will evaluate cocaine abstinence at the end of second treatment in a set of contrasts: (1) modafinil versus placebo within each initial treatment; (2) the sequence of ACT+CM with modafinil augmentation versus DC+CM with modafinil augmentation.

Hyp. 3. For initial responders, continued ACT+CM will be more effective (higher abstinence rates; < 46% relapse rate) than continued DC+CM. Logistic regression will evaluate cocaine abstinence/relapse at end of second treatment as a function of initial treatment (ACT+CM vs DC+CM).

Power. Power estimates for Hypotheses 1, 2 and 3 will use as the primary outcome (i.e., “response”), two consecutive weeks of cocaine abstinence (BE ≤ 150 ng/mL). Initial treatment response (abstinence) rates are expected to be $\sim 40\%$, based on our previous study¹² and pooled data across cocaine clinical trials⁸⁵; however we predict a difference in response rates, favoring ACT+CM over DC+CM by about 20%, constituting a clinically meaningful treatment effect. Among initial non responders, we expect at least a

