small treatment effect favoring augmentation with modafinil, based on our previous trials.^{29, 31, 32, 43} Among initial responders, we previously observed that approximately 54% remain abstinent (46% "relapse") over an extended period of treatment, up to 12 weeks. Using this estimate for the control group (DC+CM), we predict a difference in response rates, favoring continued ACT+CM by about 15%, translating into a relapse rate of about 30%. Importantly, these effect size estimates are derived from data in which missing data is counted as non-abstinence, which mirrors the way we will be treating missing data for our primary analyses.

Finally, given the uncertainty inherent in pre-existing empirical evidence and even greater uncertainty for conditional probabilities of response, prudence dictated that robust trial planning rely upon probability distributions of plausible effects that take into account the uncertainty of our predictions of effect, rather than simple point-estimates. Adoption of distributional specification of effect sizes and their associated uncertainty required implementation of a Bayesian statistical approach.

Data Simulation Model. Using the above outcome estimates, we conducted a Monte Carlo simulation study to determine predicted power for the planned analyses, taking into account uncertainty in parameter estimates. **Figure B.3.2.x** depicts the trial design with probability point-estimates and 95% Credible Limits for each treatment cell, derived from logistic regression models with vague neutral priors, averaged across $K = 500$ simulations. *Simulated results for anticipated cell sizes are shown in italics.* **Table B.3.2.x** displays estimates of power to detect any benefit ($H_A: \theta > 0$) conferred by the treatment hypothesized as being superior. All primary hypotheses demonstrate a > 80% chance of detecting 0.90 probability of benefit for a sample of $N = 160$. Also shown in **Table B.3.2.x** are the point-estimates and 95% Credible Intervals of specified effects averaging over the $K = 500$ simulations.

Summary. Using data-driven effect sizes that take into account uncertainty, simulation results indicate that with a sample size $N=160$, we have roughly 80% power for all primary hypotheses. Further, we stipulate *a priori* that a > 80% chance of treatment conferring benefit (i.e. $Pr(\Pr \theta > 0 | \text{data}) > 0.80$)

[figure not shown]

Table B.3.2.x.

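### Hypothesis 3 takes its 46% relapse target and 54% control rate from a first-positive-urine definition, but the outcome named for it is two weeks of abstinence

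*Combined protocol and SAP*

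**What the plan says.** **Benchmark.** Background Information, in the paragraph on patients who respond to initial ACT+CM, reports that 15 of 33 earlier responders relapsed, "as indicated by the first cocaine-positive urine after achieving initial abstinence". The paragraph then sets the goal: "Using 46% as a benchmark for measuring improvement". Aims and Hypotheses (item 3) and Hyp. 3 under Hypothesis testing repeat the target of under 46%.

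**Outcome.** Hyp. 3 is analysed between arms: "Logistic regression will evaluate cocaine abstinence/relapse at end of second treatment as a function of initial treatment". Relapse is not defined there. The Power section says that Hypotheses 1, 2 and 3 all use two successive abstinent weeks. The note under Overview of Study Design equates abstinent with six negative samples in a row.

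**Control rate.** The Power section takes 54% abstinent (46% relapsed), seen over as long as 12 weeks, as the DC+CM rate and adds about 15 points for ACT+CM. Table B.3.2.x gives power 0.80 for contrast 3 vs 4, at a posterior probability of 0.85 and an average effect of 0.16.

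**Missing samples and visits.** "Primary analyses will use intention-to-treat principles, with missing observations imputed as positive" (Analytic strategy). The Power section adds that "these effect size estimates are derived from data in which missing data is counted as non-abstinence". On visits: "All subjects will attend three clinic visits per week (MWF) during the 8 week second treatment period".

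**The concern.** A benchmark can be compared with a trial result only if both count the same event, over a comparable period, under the same missing-data rule. Here the event differs (any first positive against a two-week negative run) and so does the period (up to 12 weeks against 8). Whether the missing-data rule agrees is unclear, because Background counts positive urines while Power says missing data counted as non-abstinence.

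If the benchmark's definition is carried into Phase 2 with missing scored as positive, one missed visit turns a never-using responder into a relapse. On the other readings it may or may not. At stake are whether ACT+CM can be said to have brought relapse below 46%, and whether the power for Aim 3 describes the analysis that will be run.

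**Working it through.** **1. Inputs.** Phase 2 has 3 visits × 8 weeks = 24 scheduled samples. The benchmark is 15/33 = 45.5%, which the plan prints as 46% (a trivial rounding point). Phase 2 attendance is not in the documents, so per-visit attendance p = 0.98, 0.95 and 0.90 is assumed.

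**2. The plan's power figure.** Assume 80 patients per arm and Phase 1 response of 60% v 40%, giving 48 v 32 responders. With 70% v 54% abstinent and threshold 0.85, power is about 0.65 to 0.66. With 40 v 24 responders (50% v 30%) it is about 0.60. The stated 0.80 is not reproduced. The simulated cell sizes are in a figure not shown and the effect distributions are not given, so this does not prove it wrong. The point here is narrower: the text says the simulation used the outcome estimates set out above it, and for responders these are the 54% and the increment added to it.

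**3. Three readings of the Hyp. 3 outcome.** For a responder who never uses cocaine, with missing scored as positive and independent misses:
- First positive among 24: failure = 1 − p^24.
- Last six samples: failure = 1 − p^6.
- Any run of six among 24: failure = 1 − P(run of at least six attended visits), by exact recursion.

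| Assumed attendance | First positive in 24 | Last six | Any run of six |
|---|---|---|---|
| 98% | 38% | 11% | <0.1% |
| 95% | 71% | 26% | 0.1% |
| 90% | 92% | 47% | 1.2% |

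At 95%: 1 − 0.95^24 = 1 − 0.292 = 0.708, and 1 − 0.95^6 = 1 − 0.735 = 0.265.

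**4. Clustered misses.** Misses usually concentrate in some patients. With a beta-binomial at mean attendance 0.95 and ICC 0.2 (beta parameters 3.8 and 0.2), the chance of no miss in 24 is the product of (3.8+i)/(4+i) for i = 0 to 23, which is 0.66. Failure is 34% on the first-positive reading and 18% on the last-six reading.

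**5. How the readings relate.** With the same patients, samples and missing rule, anyone with no positive in 24 also passes the last-six rule, and anyone passing that has a run of six. Relapse is therefore highest on the first-positive reading and lowest on the any-run reading. If the benchmark already scored missing as positive, 46% is a lenient target for either two-week outcome, by an unknown amount. If it counted observed positives only, the missing rule pushes the other way and the direction is open.

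**6. Background against Power.** Both statements hold if missing samples were coded positive within the 15 of 33. Then at least 54% of the earlier responders missed nothing. Under independence and no use at all, that needs attendance of at least 0.54^(1/24) = 97.5% over 24 samples, or 0.54^(1/36) = 98.3% over 36. That is demanding. With clustering it is not: step 4 gives 66% with no miss at 95% attendance. The two statements need reconciling, but neither is shown to be false.

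**The case against.** The strongest reply is that the first-positive definition describes the earlier study only. No text applies it to Hyp. 3, and the Power section names the two-week outcome. That is correct. A reader might infer that the plan makes one missed visit in 24 a relapse. The documents support this only conditionally, if the benchmark's definition is carried over.

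A reader might also infer that Hyp. 3 measures attendance more than cocaine use. No Phase 2 attendance figure is given, and responders in both arms receive attendance-based CM, which rewards coming. Nor is there a formal test against 46%: the specified analysis is a between-arm logistic regression.

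A large power loss is a further tempting inference. Multiplying 54% and 69% by p^24 takes power at 0.85 from 0.63 to 0.28 at 95% attendance. If the Power section is right that missing data are already counted, this counts them twice, and the implied use-free fractions are impossible: 0.54/0.95^24 = 185%, and 0.69/0.98^24 = 112%.

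Finally, scoring missing as positive is a disclosed convention, and joint modelling, pattern-mixture models and a combined self-report and urine measure (SRPHK1) are planned. These address missingness, but they do not settle which outcome Hyp. 3 uses. The reply removes the stronger claims and leaves the mismatch: if the two-week outcome governs, a first-positive benchmark is the wrong comparator.

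**Conclusion.** The mismatch stands and should be corrected. The target and control rate for Hyp. 3 come from one definition of failure, and the outcome named for it is another. The plan fixes neither where in Phase 2 the two abstinent weeks must fall nor how an isolated missed sample counts. The choice is not cosmetic: for a never-user at an assumed 95% attendance, failure ranges from 0.1% to 71% under independent misses, and the 71% becomes 34% at ICC 0.2. These figures illustrate sensitivity to the definition. They do not predict what the trial will see, since attendance and clustering are assumed.

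As written, the under-46% target and the 0.80 power for contrast 3 vs 4 cannot be applied to the two-week outcome. The documents do not show that the Hyp. 3 result will be driven by attendance, or by how much power would change.

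**What to change.** - State one Hyp. 3 outcome: first positive, last six samples, or any run of six. Give its window, and say how an isolated or excused missed sample counts.
- Re-tabulate the 33 earlier responders under that outcome, the matching window and the same missing-data rule.
- Restate the benchmark, the DC+CM control rate and the power for contrast 3 vs 4 from that tabulation.
- Reconcile the Background definition (positive urines) with the Power statement (missing counted as non-abstinence) by saying how missing samples were handled in the 15 of 33.
- Missing scored as positive can stay as the primary rule. Report Hyp. 3 with the already planned SRPHK1 status as a sensitivity analysis for isolated misses. Making it primary is a debatable trade-off, because it brings self-report into a comparison of therapies that participants cannot be blinded to.

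The cost is a few sentences in the analysis plan, a re-tabulation of 33 existing records and a rerun of the power simulation. No visit, treatment or data collection changes.
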